9.0 Vulnerable Populations

9.1 *Vulnerable Populations:* By nature of the disease and the fact COVID-19 is a rapidly evolving pandemic, with uncertain clinical course but potentially significant morbidity and mortality, all participants enrolled in this study are considered to be vulnerable. Some participants have additional characteristics that add to this vulnerability. Our criteria for inclusion and exclusion of each of these groups is summarized below, followed by our rationale and additional safeguards built into our study design. Our group has significant experience enrolling vulnerable patients in emergency care trials, and experience with a diverse population of potential participants in high stress situations.

Population / Group	Identify whether any of the following populations will be targeted, included (not necessarily targeted) or excluded from
--------------------	--

MEDICAL PROTOCOL (HRP-590)

SHORT PROTOCOL TITLE: Randomized control trial of losartan for outpatients with COVID-19

VERSION DATE:5APR2020

	participation in the study.
Children	Excluded from Participation
Pregnant women/fetuses/neonates	Excluded from Participation
Prisoners	Excluded from Participation
Adults lacking capacity to consent and/or adults with diminished capacity to consent, including, but not limited to, those with acute medical conditions, psychiatric disorders, neurologic disorders, developmental disorders, and behavioral disorders	Included/Allowed to Participate
Non-English speakers	Included/Allowed to Participate
Those unable to read (illiterate)	Included/Allowed to Participate
Employees of the researcher	Included/Allowed to Participate
Students of the researcher	Included/Allowed to Participate
Undervalued or disenfranchised social group	Included/Allowed to Participate
Active members of the military (service members), DoD personnel (including civilian employees)	Included/Allowed to Participate
Individual or group that is approached for participation in research during a stressful situation such as emergency room setting, childbirth (labor), etc.	Included/Allowed to Participate
Individual or group that is disadvantaged in the distribution of social goods and services such as income, housing, or healthcare.	Included/Allowed to Participate
Individual or group with a serious health condition for which there are no satisfactory standard treatments.	Included/Allowed to Participate
Individual or group with a fear of negative consequences for not participating in the research (e.g. institutionalization, deportation, disclosure of stigmatizing behavior).	Included/Allowed to Participate
Any other circumstance/dynamic that could increase vulnerability to coercion or exploitation that might influence consent to research or decision to continue in research.	Excluded from Participation

9.2 *Additional safeguards:*

- *Non-English speakers:* Excluding this group would compromise the principle of justice in clinical research. For groups likely to be enrolled given our known demographics (Spanish-speaking and Somali-speaking), we will translate informed consent forms (ICF) and use professional interpreters during both the consent and follow-up periods. These interpreters are available to our group during daytime hours by telephone. *We will request the use of the Short Form Consent for non-English speaking participants, and adhere to the regulations surrounding its use. When the translated ICsF become available, they will be used for non-English speakers.*
- *Employees or students of the researcher:* To minimize the potential for coercion, any employee or student of the research will undergo screening and informed consent by study personnel, but not by the investigator who is the direct supervisor of the vulnerable participant. The screening will not be performed by the study physicians or investigators, so this group may opt out in a deidentified fashion at that stage. Furthermore, if the potential participant wants to enroll, all interactions will occur with a different study investigator (such as the other co-principal investigator. These two clinical investigators work in different departments with different staff).
- *Undervalued or disenfranchised social group:* We will assure confidentiality, that they have the right to withdraw at any time without penalty, and they have the freedom to refuse to answer questions.
- *Active members of the military (service members), DoD personnel (including civilian employees):* The status of participants of this group is not asked during the study nor known by study staff, and therefore vulnerability is not increased for anyone in this group.
- *Individual or group that is disadvantaged in the distribution of social goods and services such as income, housing, or healthcare:* We will assure that information from participants in this study will be treated with the strictest confidentiality, that participants have the right to withdraw at any time without penalty, and they have the freedom to refuse to answer questions.
- *Individual or group with a serious health condition for which there are no satisfactory standard treatments:* We will assure confidentiality, that they have the right to withdraw at any time without penalty, and they have the freedom to refuse to answer questions. We will also employ the teach-back method to ensure participants understand risks and demands of study participation.
- *Individual or group with a fear of negative consequences for not participating in the research (e.g. institutionalization, deportation, disclosure of stigmatizing behavior):* The status of participants from these groups is not asked during the study nor known by study staff, and that vulnerability is not increased for anyone in this group.

10.0 Local Number of participants

10.1 *Locations:* Enrollment will occur in the ED (or designated COVID19 areas) of MHealth Fairview Southdale Hospital, MHealth Ridges Hospital, University of Minnesota Medical Center East Bank and West Bank, Hennepin County Medical Center, Bethesda Hospital (COVID designated hospital, Mayo Clinic St. Mary's Hospital, or remotely via

the previously described methods for interested participants presenting to one of the 4 drive-thru clinics or stand-alone COVID clinic.

10.2 Number of participants: We will enroll 580 participants; this will provide adequate statistical power for testing our primary hypothesis and allows for 10% loss-to-follow-up.

11.0 Local Recruitment Methods

11.1 Recruitment Process: See section 5.0

11.2 Identification of Potential Participants: See section 5.0

11.3 Recruitment materials: Patients presenting to either the emergency department of the drive-thru clinic tested for COVID-19 will receive an informational brochure (attached as addendum) which provides information about testing, call-back, and the study. A phone number, email, and website will be created to allow participant to express interest in the study.

11.4 Payment: Patients will be eligible for a \$25 gift card for their time to return for the 15-day blood draw for renal function testing.

12.0 Withdrawal of Participants

12.1 Withdrawal Circumstances: Participants may be withdrawn from research without their consent if they develop SAEs that the investigator believes to be likely related to the study drug. Participants may also be withdrawn from the study for repeated treatment non-adherence. Participants may also withdraw from the study at any time for any reason. All data from patients withdrawn from the study will be analyzed using intent to treat principles.

12.2 Withdrawal Procedures: If patients choose to withdraw, study procedures including intervention and follow-ups will stop. Given the remote nature of this study, written notification is not required. If the patient chooses to withdraw, the study team will ask if the patient is willing to allow continued electronic medical record evaluation for the determination of study endpoints (partial withdrawal). We will also ask if the patient wishes to withdraw consent for the use of future biologic specimens. If the patient declines to participate in any component of research, no further study data will be collected, biologic samples will be destroyed, but existing study data may be used. Each of these circumstances will be documented and stored as a study document.

12.3 Termination Procedures: Upon trial termination, study outcomes will be followed until completion. Case report forms and collection templates will be maintained in paper format (when application) and electronically for 7 years in accordance with regulations. Collected data will be used for secondary analyses with approval of the principal investigators in a deidentified fashion. Data entry will be completed, checked for accuracy, and locked for analysis within 1 year of enrollment of the final patient.

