 - Patient-collected oropharyngeal swabs will be retrieved using a courier service with capacity for transport of biologic specimens to a BSL-3 laboratory (<https://www.researchservices.umn.edu/services-name/biosafety-level-3-program>). These will be stored for public health and viral research purposes.
 - Patients will be followed for 90 days to determine outcomes and the presence of any delayed adverse events. Follow-up phone contact and

electronic medical record review will determine the primary and secondary efficacy endpoints, and provide additional safety data.

1.6 *Data and specimen collection method*

- Inclusion and exclusion criteria, patient demographics, baseline comorbidities, symptoms, and validated symptom assessment measurements by patient self-report, obtained in the medical record, or obtained during an in person pre-screening visit will be collected at the time of enrollment and maintained in a RedCap database. In addition, electronic consent forms will be maintained in a University of Minnesota RedCap database with established functionality currently used by our group for this purpose in our group. The database, with the currently approved eConsent policy, and is HIPAA compliant.
- Every other day follow-ups will be recorded by study personnel into a RedCap database and will include self-reported AEs and medication adherence and maximum daily temperature. On days 0, 4 and 10, a previously validated patient-reported outcomes measurement information system (PROMIS) dyspnea survey and SF-12 (survey's attached in supplement). In the event the patient is not available or contacted on the day of survey administration, surveys administered +/- 1 day will be considered before this data point is considered missing. The following datapoints will also be collected, if available:
 - Name
 - Date of birth
 - Medical record number (if applicable)
 - Phone number
 - Email address
 - Age
 - Gender
 - Race
 - Ethnicity
 - Insurance status (if available)
 - Zip code
 - Location of initial sample collection for diagnosis
 - Location of assessment
 - Date and time of initial sample collection for diagnosis
 - Date and time of positive test result for COVID-19
 - Date of first symptoms
 - Date of first fever (temperature >101.5)
 - Vital signs at presentation (if recorded)
 - Clinical laboratory results at presentation (if recorded)

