 - Patient-reported comorbidities [hypertension (requiring or not requiring medication), diabetes mellitus (insulin or non-insulin dependent), coronary artery disease, myocardial infarction, congestive heart failure (with preserved or reduced ejection fraction, if known), pacemaker or AICD, asthma (with or without emergency department evaluation and / or hospital admission in the past year), chronic obstructive pulmonary disease, chronic bronchitis, chronic steroid use, history of transplant (with type),

MEDICAL PROTOCOL (HRP-590)

SHORT PROTOCOL TITLE: Randomized control trial of losartan for outpatients with COVID-19

VERSION DATE:5APR2020

arrhythmias including atrial fibrillation, dialysis, angina, pulmonary hypertension and obstructive sleep apnea, renal disease, liver disease, tobacco and alcohol use history, recent pregnancy or breastfeeding history, height and weight]

- Self-reported home medications [antihypertensives, insulin, non-insulin diabetes medications, corticosteroids (inhaled or systemic), other immunosuppressants hydroxychloroquine, other COVID-directed treatments] or home oxygen use
- Use of outpatient COVID-directed treatments (such as hydroxychloroquine, Tylenol, ibuprofen, azithromycin, or others)
- PROMIS Pool v1.0 Dyspnea Characteristics Survey (5 question Likert scale survey) (attached) with date/time of administration
- Short form 12 (SF-12) health survey (attached) with date/time of administration
- Oropharyngeal swab every third day (performed, yes or no)
- Lowest home blood pressure daily
- Highest home temperature daily
- Medication adherence
- Hospital admission (with date, if applicable)
 - a. If admitted: initial vital signs, initial and highest method of respiratory support (oxygen by nasal cannula, facemask, high flow nasal cannula, CPAP, BIPAP, endotracheal intubation, ECMO), initial and worst measures of organ failure (SOFA score), and initial and worst markers of cardiac injury (troponin, BNP/pro-BNP. CXR or CT chest results will be recorded. If patients are admitted to non-MHealth or HCMC hospitals, we will contact the patient to obtain permission to request data from their hospitalization.
- Date of death (if applicable)
- Study withdrawal, with date and time (if applicable)

- Final outcome follow-ups will be determined through a combination of patient report, electronic medical record review, and review of the social security death index (SSDI).

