4.3 *Investigational new drug.* The study will undergo pre-IND review with the Food and Drug Administration to determine the need for an investigational new drug assessment, and will be assigned an IND number if required.

4.4 *Timing of the intervention:* Treatment will continue for 10 days or attainment of the primary outcome (hospital admission).

4.5 *Duration of study participation:* The final follow-up will occur at 90 days after randomization to determine episodes of delayed hospitalization. Data analysis is expected to be completed within 1 year of enrollment of the final patient.

4.6 *Drug Handling, blinding, and randomization:*

Fairview Investigational Drug Services (IDS), part of M Health Fairview will oversee the preparation of treatment drug and placebo. Identical pills (#20) will be placed in identical

MEDICAL PROTOCOL (HRP-590)

SHORT PROTOCOL TITLE: Randomized control trial of losartan for outpatients with COVID-19

VERSION DATE:5APR2020

bottles with a deidentified study number coded by site and patient number (e.g. 01-001, 02-001, etc.). A site-specific randomization schema will be created (each site will undergo permuted block randomization with random block sizes stratified by site and age). Given significant differences in outcome by age, patients will be randomized by age strata (≥ 50 , < 50). Randomization allocation will be 1:1. IDS will not be blinded to patient randomization. All other members of the study, the participants, and the clinical care team will be blinded to treatment allocation.

4.7 *Provision of study drug to patients*: Following randomization, a courier service will ship drugs to study participants within 24 hours of randomization. Each dispensing will contain 20 capsules, enough to complete the 10-day therapy

4.8 *Study unblinding*: MHealth Fairview, East bank Inpatient Pharmacy UMMC campus, will hold the blind for all subjects on study. In the event of an emergency and unblinding is necessary, study staff can contact [contact], option 1, then option 2. This information is included on each label.

4.9 *Biosafety*: N/A. The intervention is not a biohazard.

4.10 *Stem Cells*: N/A

4.11 *Fetal Tissue*: N/A

4.12 *Use of radiation*: N/A

4.13 *Use of Center for Magnetic Resonance Research*: N/A

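### Section 12.1 lets participants be withdrawn from the study, instead of only taken off drug, and nothing secures their day-15 hospitalization status afterwards

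*Combined protocol and SAP*

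**What the plan says.** Section 12.1 gives two grounds for withdrawal that do not come from the participant. The first is adherence: "Participants may also be withdrawn from the study for repeated treatment non-adherence". The second is safety: participants may be "withdrawn from research without their consent if they develop SAEs that the investigator believes to be likely related to the study drug". Both are permissive. Neither is limited to stopping drug, and neither is linked to collecting the primary endpoint. The section then states: "All data from patients withdrawn from the study will be analyzed using intent to treat principles".

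Section 12.2 covers a different situation: "If patients choose to withdraw, study procedures including intervention and follow-ups will stop". The offer of continued record review (partial withdrawal) sits in the same paragraph and is worded for the same patients.

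Section 4.4 ends treatment at day 10 or at hospital admission. It names no state in which a participant is off drug but still followed.

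On sources, Section 1.5 names follow-up phone contact together with record review. Section 1.6 says: "Final outcome follow-ups will be determined through a combination of patient report, electronic medical record review", plus the death index. The events table (5.5) lists the hospitalization check among the outpatient study procedures.

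**The concern.** The primary endpoint is hospital admission by day 15, and patient contact is one of its stated sources. On its ordinary meaning, withdrawal from the study ends that contact. The intent-to-treat sentence governs how data already held are analyzed. It cannot supply a day-15 status that nobody collected, and Section 15.1 has no rule for a missing primary outcome.

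Non-adherence and drug-related SAEs both occur after randomization and may reflect the drug or a worsening illness. Outcomes lost for those reasons are not safely ignorable, even if both arms lose the same number. Unlike ordinary loss to follow-up, the protocol itself authorizes this loss. It is also avoidable: stopping drug meets the safety purpose of the SAE clause, and removing non-adherent participants serves no purpose in an intent-to-treat comparison.

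**Working it through.** **1. Which provisions reach these participants?**

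- *Section 12.2.* Both the stop rule and the partial-withdrawal offer are conditional on the patient choosing to withdraw. For withdrawals under the two 12.1 grounds, 12.2 neither ends follow-up nor guarantees it.
- *Record review (1.5, 1.6).* There is no exception for withdrawn participants, so it may continue. But Section 4.1 accepts that a participant may be admitted outside the participating hospitals, and for admissions outside the study's own hospitals Section 1.6 has the team contact the patient for permission to request the data. Record review without contact can therefore miss such admissions.
- *SAE collection (18.2).* It runs for 15 study days and counts admissions, again with no exception. But adverse-event information is sought at contacts with the subject, and no section says contacts continue after a 12.1 withdrawal.
- *SAE ground.* An SAE that is itself an admission already meets the endpoint. The exposed group is therefore mainly the non-adherent.

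**2. Size of the possible bias.** Inputs: 15% hospitalization (15.2), taken in both arms so that there is no true effect, and 290 per arm (15.2). Assumed, because the documents give no figure: a fraction *w* = 1-5% withdrawn with outcome unknown (about 3 to 15 of 290), of whom a fraction *r* = 5-30% are hospitalized. Then

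observed rate = (0.15 − *w·r*) / (1 − *w*).

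| *w* | observed if *r* = 5% | observed if *r* = 30% | shift if one arm only | gap if 5% in one arm, 30% in the other |
|---|---|---|---|---|
| 1% | 0.1495/0.99 = 15.10% | 0.1470/0.99 = 14.85% | +0.10 or −0.15 points | 0.25 points |
| 3% | 0.1485/0.97 = 15.31% | 0.1410/0.97 = 14.54% | +0.31 or −0.46 points | 0.77 points |
| 5% | 0.1475/0.95 = 15.53% | 0.1350/0.95 = 14.21% | +0.53 or −0.79 points | 1.32 points |

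The shift can favour either arm. It is zero throughout if *r* = 15%. It is also zero if both arms have the same *w* and the same *r*. A far more extreme assumption, 10% withdrawn on losartan and 2% on placebo with *r* = 45%, gives 0.105/0.90 = 11.67% against 0.141/0.98 = 14.39%, or 2.7 points. Nothing in the documents suggests rates of that order.

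**3. Power.** Section 15.2 plans 15% vs 7%, two-sided 0.05, 80% power, 264 per group. With pooled rate 0.11:

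*n* = [1.960·√(2·0.11·0.89) + 0.842·√(0.15·0.85 + 0.07·0.93)]² / 0.08² = 238.9, so 239.

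Continuity-corrected: (*n*/4)·[1 + √(1 + 4/(0.08·*n*))]² = 263.4, so 264, the plan's figure.

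Section 15.1 names the chi-square test and no correction. Without one, power is 83.4% at 261 per arm (290 × 0.90) and 81.1% at 246 (a further 5% of 290 lost).

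**The case against.** The strongest reply is that silence is not an instruction to lose outcomes. A reader might infer that 12.2 orders follow-up to stop for anyone withdrawn under 12.1. It does not: its stop rule is confined to patients who choose to leave. A reader might also infer that partial withdrawal is the only off-drug status with any ascertainment. The text does not support that either. Section 18.2 lists drug discontinuation beside more frequent follow-up as ways to manage a laboratory abnormality, and Section 5.4 does not make calls conditional on taking drug. An investigator's decision also does not revoke the participant's agreement to record access. SAE collection to day 15 and follow-up of unresolved adverse events both continue on their face, and the intent-to-treat sentence shows that withdrawn participants were meant to stay in the analysis.

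All of that stands, and it narrows the point without removing it. None of these provisions says that a participant withdrawn from the study is still telephoned, and without contact an outside admission can go unseen.

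The reply is also right on size. Every withdrawal rate above is assumed. The 1.3-point extreme needs a sixfold difference in risk between the withdrawn in the two arms of a blinded trial.

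**Conclusion.** The point holds as a correctable weakness in a stated rule. Section 12.1 permits removal from the study where stopping drug would suffice, and day-15 ascertainment afterwards is left unsecured, chiefly for non-adherent participants admitted to non-participating hospitals. The effect is probably small: about 0.1 to 1.3 points in either direction under the assumed 1-5% withdrawal and 5-30% risk, against a planned difference of 8, and none if the withdrawn have average risk.

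A reader might infer that the trial has no reserve for such losses, since 290 less 10% leaves 261 against the stated 264. The documents do not support this. The 264 reproduces only with a continuity correction that 15.1 does not specify, the uncorrected requirement is 239, and power stays above 80% after a further 5% loss. Nor does 15.2 say that its 10% allowance excludes these withdrawals. The case for changing the text rests on the loss being avoidable at almost no cost.

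**What to change.** In 12.1, delete non-adherence as a ground for study withdrawal. State that non-adherence or a drug-related SAE leads to stopping study drug only, with all scheduled calls and outcome ascertainment continuing unless the participant withdraws consent. Add this drug-stop status to 4.4.

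Optional extras: in 12.2, offer patients who want to leave the choice of stopping drug but keeping the calls before offering record review alone; and record the date and reason of the last dose on the existing calls.

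Cost: protocol wording, possibly a matching consent sentence (the consent form was not among the reviewed text), and a few more calls to participants off drug, within the existing schedule. Sample size and the primary test do not change. Keeping off-drug participants in the analysis slightly dilutes the contrast between arms, which an intent-to-treat analysis already accepts.
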